We estimated a pre-defined 8-point non-inferiority margin, based on a significant effect of the COGNI-TRAcK in inducing an about 8-point mean increase at SDMT score (with respect to a sham intervention). Accordingly, 35 subjects per arm are required to ensure, with an approximately 85%-power level, that the lower limit of a one-side 95% confidence interval will be above the pre-defined non-inferiority margin. Therefore, considering also a drop-out rate of 25%, a total of 132 subjects should be enrolled.

Statistical methods

All analysis will be based on the intention-to-treat principle using the fully analysis dataset including all randomized patients. Missing data will be handled by multiple imputation method. Continuous data will be analyzed by parametric and non-parametric RM-ANOVAs with effect size estimation. The time-to-event data will be analyzed by Kaplan-Meier curves and Log-Rank test with a factor for treatment group.

An interim analysis will be conducted when at least 50% of the estimated sample size will complete the 8-week intervention period.

Study objectives

Primary objective	Primary endpoint
To demonstrate not inferior efficacy of exergames over COGNI-TRAcK and superior efficacy of both interventions over sham in improving sustained attention and information processing speed	Change at the SDMT from baseline to Week 8
Secondary objectives	Secondary endpoints
To demonstrate not inferior efficacy of exergames over COGNI-TRAcK and superior efficacy of both interventions over sham in improving cognitive functions	Change at the BICAMS and SCWT from baseline to Week 8
Additional objectives	Additional endpoints
To demonstrate not inferior efficacy of exergames over COGNI-TRAcK and superior efficacy of both interventions over sham in reducing the impact of MS on: - cognitive-motor interference - activities of daily living - fatigue - work productivity	Change of dual-task cost of walking and balance as estimated by the 2MWT and static posturography in dual-task vs. single-task condition from baseline to Week 8 Change at the MSIS-29 from baseline to Week 8 Change at the MFIS from baseline to Week 8 Change at the WPAI:MS from baseline to Week 8
Exploratory objectives	Exploratory endpoints
To demonstrate not inferior efficacy of exergames over COGNI-TRAcK and superior efficacy of both interventions over sham on: - physical activity - adherence	Physical activity measured by wearable actigraph Percentage of training completed at home

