No pharmacological treatment is strictly forbidden; however, patients are encouraged to not start pharmacological treatments that can potentially impact on cognition, namely antidepressants, dalfampridine, nabiximols, modafinil, amantadine, dopamine-agonists.

Steroid administration due to MS relapse or any symptomatic drug initiation due to any MS-related symptom should be considered as an AE.

Patients are encouraged to not start any other type of physiotherapy or rehabilitation during the study period, but they are encouraged to continue his/her physiotherapy or rehabilitation program if started at least 3 months before the study enrolment.

STATISTICAL PLAN

Sample size estimation

Overall, we will randomize **126 patients** (considering even a 20% drop-out rate), based on two previously published studies that have found:

- (i) a significant effect of an home-based cognitive training using the [name]® Brain Training that promoted an about 8-point mean increase at SDMT score (with respect to wait-list group) [53];
- (ii) a significant effect of adaptive COGNI-TRAcK that promoted an about 8-point mean increase at SDMT score (with respect to a sham intervention) [24];
- (iii) a 50%-difference in proportions of responders (10/14 versus 3/14 in adaptive COGNI-TRAcK group and sham COGNI-TRAcK group, respectively) [24], according to a responder definition of SDMT change approximating 4 points or 10% in magnitude [28].

For the non-inferiority comparison, the null hypothesis is that the intervention with exergames is inferior to adaptive COGNI-TRAcK, while the alternative hypothesis is that the intervention with exergames is non-inferior to adaptive COGNI-TRAcK by a pre-defined amount of SMDT score.

If there is truly no difference between exergames and adaptive COGNI-TRAcK, then 35 patients per arm are required to ensure, with a statistical power of approximately 85%, that the lower limit of a one-sided 95% confidence interval (or equivalently a 90% two-sided confidence interval) will be above the predefined non-inferiority margin of 8-point change in SDMT.

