For the superiority comparison, the null hypothesis is that the intervention with adaptive COGNI-TRAcK is not superior to sham COGNI-TRAcK, while the alternative hypothesis is that the intervention with adaptive COGNI-TRAcK is superior to sham COGNI-TRAcK in increasing the proportion of responders as afore defined. Enrolling 35 patient per arm will ensure a more than 95% power in detecting a statistical significance between-group difference of 50% at two-sided alpha level of 5%.

Statistical analysis

All analysis will be based on the intention-to-treat principle using the fully analysis dataset including all randomized patients. Missing data will be handled by multiple imputation method, with the assumption that some data will be missed completely at random.

Efficacy analyses: efficacy data will be analyzed by parametric and/or non-parametric Repeated Measures Analyses of the Variance (RM-ANOVAs) with effect size estimation. In each analysis, we will consider as dependent variable all measures or score derived from study assessments; the three study visits (Baseline, Week 8 and Week 16) as within-subject factors; and intervention arms (exergames, adaptive COGNI-TRAcK and sham COGNI-TRAcK) as between-subject factors. Effect sizes will be estimated as Cohen's F-squared, rated as small, medium, and large for values of 0.02, 0.15, and 0.35, respectively [54].

Safety data regarding time to first accidental falls will be analyzed as time-to-event data by Kaplan-Meier curves and Log-Rank test with a factor for intervention arms.

Safety analyses: data regarding the occurrence of adverse events during the intervention period and the follow-up period will be analyzed by the Chi-squared test comparing the independent distribution of events according to intervention arms.

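### Non-inferiority is an objective at every endpoint level, but only SDMT has a margin and the stated analysis tests difference, so the plan gives no valid basis for the claim elsewhere

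*Protocol*

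**What the plan says.** The Study objectives table in the Protocol Synopsis uses one confirmatory formula at four levels. At the primary level it concerns SDMT. At the secondary level (BICAMS and SCWT) it reads "To demonstrate not inferior efficacy of exergames over COGNI-TRAcK and superior efficacy of both interventions over sham in improving cognitive functions". At the additional level (dual-task cost of walking and balance, MSIS-29, MFIS, WPAI:MS) it reads "To demonstrate not inferior efficacy of exergames over COGNI-TRAcK and superior efficacy of both interventions over sham in reducing the impact of MS on". The exploratory level (physical activity and adherence) repeats it. The Study design statements, in the Synopsis and again under Methods, also place cognitive-motor interference inside the non-inferiority hypothesis of the trial.

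The margin appears in two places, both in SDMT units. The Synopsis has "We estimated a pre-defined 8-point non-inferiority margin, based on a significant effect of the COGNI-TRAcK in inducing an about 8-point mean increase at SDMT score". The Sample size estimation section of the Statistical Plan has "predefined non-inferiority margin of 8-point change in SDMT", and its alternative hypothesis is that exergames are "non-inferior to adaptive COGNI-TRAcK by a pre-defined amount of SMDT score". The decision criterion given there is that "the lower limit of a one-sided 95% confidence interval (or equivalently a 90% two-sided confidence interval") lies above that margin.

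For the analysis itself, the Statistical analysis section says that "efficacy data will be analyzed by parametric and/or non-parametric Repeated Measures Analyses of the Variance", with every measure derived from the assessments as a dependent variable, visit as the within-subject factor and arm as the between-subject factor. The section on the pre-planned significance level applies a two-sided 0.025 to all analyses.

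**The concern.** A non-inferiority conclusion needs a margin on the scale of the endpoint and a rule that compares a confidence limit with it. For the endpoints other than SDMT the protocol has neither. An 8-point SDMT margin cannot be carried over to word-list recall, Stroop performance, postural sway, questionnaire scores or the percentage of training completed. The analysis that is stated asks whether the arms differ, and failure to show a difference is not evidence that exergames are no worse by a relevant amount.

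What is at stake is the reporting of most of the trial's outcomes. The protocol commits to demonstrating something that its own analysis cannot demonstrate. The SDMT objective has a margin and is outside this point.

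**Working it through.** **1. Objectives set against margins and analysis**

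| Level | Measures | Non-inferiority objective | Margin stated | Analysis stated |
|---|---|---|---|---|
| Primary | SDMT | yes | 8 points | RM-ANOVA; confidence-limit rule in the sample-size text only |
| Secondary | SDMT as part of BICAMS | yes | 8 points (same measure) | as above |
| Secondary | CVLT2, BVMT-R, SCWT | yes | none | RM-ANOVA |
| Additional | dual-task cost, MSIS-29, MFIS, WPAI:MS | yes | none | RM-ANOVA |
| Exploratory | physical activity, adherence | yes | none | RM-ANOVA |
| Safety | falls, adverse events | no (worded differently) | not applicable | log-rank, chi-squared |

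**2. The plan's own figure.** The 35 per arm is for SDMT: margin 8, true difference 0, one-sided 5%, power about 85%. No SD is given, so the figure can only be solved backwards:

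SD = 8 / [√(2/35) × (1.645 + 1.036)] = 12.48.

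An SD of about 12.5 points therefore reproduces 35 per arm. This sizing says nothing about the other endpoints, for which neither a margin nor an SD is stated.

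**3. Illustration: what a non-significant difference would be worth.** The protocol does not state this reading. The calculation only shows why it could not stand in for a margin.

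- Evaluable number: 35 per arm (Sample size estimation). For comparison, 126/3 = 42 randomised per arm in the same section, and 132/3 = 44 in the Synopsis.
- Threshold: two-sided 0.025 (significance-level section), with 0.05 as a variant.
- Assumed, not in the protocol: true deficits of 0.3 and 0.5 SD, and a two-sample t-test as a stand-in for the exergames versus adaptive contrast.

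The non-centrality is d × √(n/2) with 2n − 2 degrees of freedom, and P(non-significant) is the non-central t probability between −t_crit and +t_crit. For n = 35 at 0.025, df = 68 and t_crit = 2.292:

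- d = 0.3: 0.3 × √17.5 = 1.255, giving P = 0.843.
- d = 0.5: 0.5 × √17.5 = 2.092, giving P = 0.575.

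| n per arm | d = 0.3, at 0.025 | d = 0.5, at 0.025 | d = 0.3, at 0.05 | d = 0.5, at 0.05 |
|---|---|---|---|---|
| 35 | 84% | 57% | 76% | 46% |
| 42 | 81% | 49% | 73% | 38% |
| 44 | 80% | 47% | 71% | 36% |

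A margin-based test at one-sided 5% would wrongly declare non-inferiority 5% of the time when the true deficit equals the margin.

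**4. Could margins simply be added at this size?** With assumed margins in SD units, true difference 0 and one-sided 5% (normal approximation), power at 35 per arm is 21% for 0.2 SD, 35% for 0.3, 51% for 0.4 and 67% for 0.5. Reaching 85% would take 360, 160, 90 and 58 per arm respectively.

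**The case against.** The strongest reply is that margins and interval rules for non-primary endpoints are commonly left to the statistical analysis plan, which is not at hand. That stands as far as the absence of margins alone goes. It does not remove the mismatch, because the protocol fixes both the aim of demonstrating non-inferiority and an analysis for all measures that cannot do so.

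A reader might go further and infer that the trial would declare exergames not inferior whenever the difference is non-significant. The document does not support that. No sentence says so, and the one non-inferiority rule it contains, for SDMT, correctly compares a confidence limit with a margin. Effect sizes are also promised, as Cohen's f-squared. The accurate statement is that no valid basis is given, and the percentages above describe a decision rule that the protocol does not state.

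Three narrower objections also stand:

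- It is not true that every secondary endpoint lacks a margin, because SDMT is a component of BICAMS.
- RM-ANOVA is not the only model named. For endpoints without a defined clinically relevant change, the predictors paragraph specifies an ANCOVA with arm as a fixed factor. It would yield an adjusted arm difference, but it serves the predictor question and brings no margin.
- The 0.025 is derived from the two comparisons with sham, so its use for exergames versus adaptive COGNI-TRAcK rests on the phrase that covers all analyses. The 0.05 columns show that the picture does not depend on this.

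That these are non-primary endpoints of a phase II trial limits the severity. It does not make the confirmatory wording right.

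**Conclusion.** The point holds in this form. For CVLT2, BVMT-R, SCWT and all additional and exploratory endpoints, the protocol sets out to demonstrate non-inferiority without a margin, hypotheses or an interval rule, and states an analysis that tests difference. This follows from the text alone and does not depend on any assumed SD or sample size.

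The size is illustrative only. If non-significance were taken as non-inferiority, true deficits of 0.3 and 0.5 SD would pass about 84% and 57% of the time with 35 evaluable per arm at 0.025 (81% and 49% with 42). Those figures rest on the assumed deficits and on a t-test approximation. The sample size and the primary SDMT objective are not affected by this point, and neither is the safety objective.

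**What to change.** - Restrict the non-inferiority claim to SDMT, and state in the Statistical analysis section that it is tested by the confidence limit against its margin. At present that rule appears only in the sample-size text.
- Reword the other secondary, additional and exploratory objectives to compare or estimate. Make the same change to the cognitive-motor interference part of the hypothesis in both Study design statements, so that objectives and hypothesis agree.
- For those endpoints, report the exergames-minus-adaptive difference with a confidence interval at a stated level, and draw no non-inferiority conclusion.
- If the claim is to be kept for a particular endpoint, pre-specify a justified margin and an interval rule for it, and acknowledge the power that the planned size provides.

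The cost is rewording the objectives and the hypothesis and adding one sentence each on testing and reporting. Visits, conduct and sample size do not change. The sponsor gives up non-inferiority claims that the stated analysis cannot support.

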Safety objectives	Safety endpoints
To demonstrate the safety of exergames and COGNI-TRAcK over sham on the risk of: - accidental falls - adverse events	Time from randomization to the first accidental fall Proportion of patients with at least an adverse event from baseline to Week 8 and to Week 16

INTRODUCTION

Background and rationale for conducting the study

Cognitive impairment is common in people with multiple sclerosis (MS), frequently involving domains such as information processing speed, episodic memory, sustained attention, concentration and aspects of executive functions [1],[2]. Cognitive dysfunction can affect patients at any stage of the disease, from radiologically isolated syndrome to later phases of MS [3],[4].

There is no effective pharmacological treatment to manage cognitive impairment in MS [5]. Therefore, rehabilitation remains the only strategy to limit the impact of this dysfunction on quality of life. Encouraging results have been reported with computer-assisted training specifically focused on information processing, attention, and executive functions and performed with dedicated software [6]. Unfortunately, the time and costs of these cognitive rehabilitative programmes limit their applicability in the real life.

To increase the complexity of MS management, very often people with MS have coexisting cognitive and motor deficits and require both cognitive and motor rehabilitation. **Therefore, providing a single rehabilitative strategy that can address cognitive and motor issues remains highly desirable.**

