Predictors of outcomes: logistic regression analyses will test if the achievement of a clinically relevant change in the pre-planned endpoints is predicted by scores derived from CRIQ, HLAQ and TCI, after controlling for a set of baseline covariates including sex, age, disease duration, EDSS score, performance on the explored task. For those endpoints lacking of a definition of clinically relevant change, we will adopt Analyses of Covariance (ANCOVAs) with immediate post-training score as dependent variables, intervention arm as fixed factor and a set of baseline covariates including sex, age, disease duration, EDSS score, baseline performance on the explored task, as well as scores derived from CRIQ, HLAQ and TCI as covariates of interest.

Pre-planned statistical significance level

Exergames and adaptive COGNI-TRAcK will be compared with sham COGNI-TRAsK as placebo-analogue arm. Therefore, all analysis will be corrected with Bonferroni adjustment for multiple comparisons of two-sided tests, giving a two-sided significant p-value of 0.025.

Interim analysis

An interim analysis will be conducted when at least 50% of the estimated sample size will complete the 8-week intervention period.

STUDY GOVERNANCE AND OVERSIGHT

Steering committee

The steering committee shall comprise the Principal Investigator (PI) and all the co-investigators reported in this study protocol.

The steering committee will be responsible for the overall design, interpretation, supervising and reporting (presenting at national and international congresses and publishing in peer-reviewed journals). Members of steering committee will be also responsible for providing clinical guidance on study implementation and conduct in their respective sites.

Data Monitoring

An independent Data Monitoring Committee (DCM) will be appointed to review the overall conduct of the study, with particular attention to eligibility criteria, randomization, and collection of efficacy and safety data. The DCM will have access to the individual treatment codes while the study is ongoing; therefore, if DMC expresses safety concerns, appropriate information will be sent to the PI, regulatory authorities and study funder Associazione Italiana Sclerosi Multipla (AISM).

The DCM is also responsible for ensuring the maintenance of blinding and integrity of the study.

ETHICAL AND REGULATORY REQUIREMENTS

Ethical conduct of the study

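### The safety objective promises to demonstrate safety over sham, but the planned difference tests, with no margin or confidence limit, cannot show that excess risk is absent.

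*Protocol*

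**What the plan says.** In the Protocol Synopsis, under Study objectives, the safety objective reads "To demonstrate the safety of exergames and COGNI-TRAcK over sham on the risk of" accidental falls and adverse events. Its endpoints are time from randomization to first accidental fall and "Proportion of patients with at least an adverse event from baseline to Week 8 and to Week 16".

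The Statistical analysis section gives the analyses. For falls: "Safety data regarding time to first accidental falls will be analyzed as time-to-event data by Kaplan-Meier curves and Log-Rank test", with a factor for arm. Adverse events "will be analyzed by the Chi-squared test comparing the independent distribution of events according to intervention arms". The section on the pre-planned significance level applies a Bonferroni correction to all analyses, "giving a two-sided significant p-value of 0.025".

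The protocol states no expected fall or adverse-event rate, no acceptable excess risk, no confidence limit for a safety contrast and no power for safety. Its one margin, 8 SDMT points with a one-sided 95% confidence limit, belongs to the efficacy comparison of exergames with adaptive COGNI-TRAcK.

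**The concern.** Both planned tests take equal risk as the null hypothesis. Rejecting it shows a difference; failing to reject it does not show that a harmful difference is absent. A claim that a training carries no important excess risk needs an upper limit on that excess. The protocol uses this logic for its SDMT non-inferiority claim but not for safety.

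The number of patients was set by SDMT, not by falls or adverse events. Falls are the hazard the protocol singles out for these minimally assisted home programmes, and balance games are the intervention of interest. If a non-significant test were reported as safety demonstrated, the statement could support unsupervised use while a doubled fall hazard was still compatible with the data.

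**Working it through.** **Inputs from the protocol.** Allocation is 1:1:1. The Sample size section says "35 patients per arm are required to ensure, with a statistical power of approximately 85" percent, and randomizes 126 in total, "considering even a 20% drop-out rate": 3 × 35 = 105, 105 × 1.20 = 126, or 42 per arm. The synopsis gives 132, or 44 per arm. The analysis set is all randomized patients, so 42 is used here. Alpha is two-sided 0.025; 0.05 is shown for comparison.

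**Assumptions.** Sham risk over 16 weeks of 10% to 40%, because no rate is given. The excess is in exergames only, with adaptive COGNI-TRAcK equal to sham. Fall times are exponential, censored at 16 weeks.

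**The plan's own figure.** No safety power is stated. The nearest figure with complete inputs is the superiority power: responders 10/14 vs 3/14, 35 per arm, two-sided 5%. This gives 99.5%, consistent with the stated value of more than 95%. It concerns a 50-point difference on a cognitive endpoint and says nothing about safety.

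**Log-rank test, hazard ratio 2.** With sham risk p, the exergames risk is 1 − (1 − p)². Simulated three-arm test, 42 per arm, accurate to about 2 percentage points:

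| Sham risk | Exergames risk | Missed at 0.025 | Missed at 0.05 |
|---|---|---|---|
| 10% | 19% | 87% | 79% |
| 20% | 36% | 70% | 61% |
| 30% | 51% | 56% | 45% |
| 40% | 64% | 45% | 35% |

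A pairwise check with Schoenfeld's formula, exergames vs sham at 0.025, gives power of 15/29/41/52%, so misses of 85/71/59/48%. Events needed for 80% power are 4(z_α/2 + z_β)² / (ln 2)²:
- at 0.05: 4 × (1.960 + 0.842)² / 0.480 ≈ 66
- at 0.025: 4 × (2.241 + 0.842)² / 0.480 ≈ 80

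At a sham risk of 20%, the two arms are expected to yield 42 × (0.20 + 0.36) ≈ 23.5 first falls.

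**Chi-squared test, doubled proportion with at least one adverse event.** Simulated three-arm test, 42 per arm:

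| Sham vs exergames | Missed at 0.025 | Missed at 0.05 |
|---|---|---|
| 10% vs 20% | 82% | 75% |
| 20% vs 40% | 56% | 44% |
| 30% vs 60% | 24% | 16% |

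With 35 per arm, pairwise power at 0.025 is 14/34/62%, so misses of 86/66/38%.

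**What a result with no observed difference would exclude.** With equal observed risks of 20% in 42 per arm, the one-sided 95% upper bound on the risk difference is 1.645 × √(2 × 0.20 × 0.80 / 42) = 0.144, or 14 points. The upper limit of a two-sided 95% interval is 1.96 × 0.0873 = 0.171, or 17 points. With 8 first falls in each arm and an estimated hazard ratio of 1, the one-sided 95% upper bound is exp(1.645 × √(2/8)) = 2.28.

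**The case against.** Six points can be made for the protocol.

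1. A reader might infer that the plan treats a non-significant test as proof of safety. No section says so; the protocol names the tests and is silent on how a null result will be read. Taken literally, showing something over sham could even mean fewer events than sham, and a non-significant result would then fail the objective. This stands, and the point is limited to the gap between objective and analysis.
2. The verb is weak evidence of confirmatory intent. Every tier of objectives, including the exploratory one, opens with it, and the rationale for the endpoints describes falls and adverse events as providing data on safety. This also stands. It makes rewording the natural remedy.
3. A reader might infer that an important excess is in general more likely to be missed than found. The figures do not support that across the board: 30% vs 60% is missed in only 16% to 24% of trials, and a hazard ratio of 2 at 40% sham risk in 35% to 45%.
4. Interval estimates for safety are often left to the statistical analysis plan. Their absence alone would be no finding. The protocol, however, fixes both an objective and tests that cannot meet it.
5. Safety does not rest on two p-values. All randomized patients are analysed, telephone follow-up collects safety data after loss to follow-up, Kaplan-Meier curves describe fall risk by arm, and an independent committee has access to treatment codes. These protect participants and data, but they do not change what the final tests can support.
6. Sizing a phase II trial on its primary endpoint is ordinary practice. Agreed; no larger sample is asked for.

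**Conclusion.** The point holds as a mismatch: the objective claims more than the difference tests can show, and the protocol supplies no margin or confidence limit to close the gap. On the assumptions above (sham risks of 10% to 40%, excess in exergames only, 42 per arm, two-sided 0.025), sensitivity to a doubling is poor at low to moderate risk and adequate only for adverse events at high risk. The log-rank miss rate for a hazard ratio of 2 runs from about 87% down to 45%; the chi-squared miss rate for a doubled risk runs from about 82% at 10% sham risk to 24% at 30%. The protocol's own background, with few or minor adverse events and no increased fall risk reported in pilots, points towards the low-risk end, but it gives no rate to fix this. The primary analysis and the sample size are not affected.

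**What to change.** Reword the safety objective as estimating the excess risk of falls and adverse events versus sham. In the Statistical analysis section, for exergames vs sham and for adaptive COGNI-TRAcK vs sham, report the risk difference in patients with at least one adverse event and the hazard ratio for first fall, each with a 95% confidence interval. Keep the log-rank and chi-squared tests as descriptive. State that any safety conclusion will be worded by the upper confidence limit, that is, by the excess the data exclude, and not by non-significance.

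The cost is a change of wording and two interval estimates per comparison from data already collected, with no extra patients or visits. The trial gives up a claim of demonstrated safety that it could not have supported.
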